9.3. Treatment Compliance

[figure not shown]
CYNK-001 is to be administered IV at the clinical study site. Study personnel will review the dosing treatment allocation and ensure treatment is administered according to the subject's treatment plan. Treatment compliance will be noted on the appropriate CRFs and source records based on administration records.

- Dose reductions are not permitted in this study.
- Dose delays are permitted. See [Section 6.5](#)
- Concomitant therapies
 - Blood product transfusions should not occur within 24 hours prior to and/or 24 hours after CYNK-001 infusion.
 - Use of steroids is permissible if clinically indicated and at the discretion of the treating physician.

10. STUDY DRUG MATERIALS AND MANAGEMENT

For the second and third doses (6×10^8 cells each) inspect the contents of the prepared

11. ASSESSMENT OF EFFICACY

This study will explore the potential clinical efficacy of CYNK-001 by evaluating:

- **OSCI**: OSCI will be recorded daily in hospital and outpatient by phone contact. See [Appendix D](#) for the definition of the ordinal scale for clinical improvement.
- **Clearance of SARS-CoV-2**: defined as the time from the date of randomization to the clearance of SARS-CoV-2 by rRT-PCR by two negative results at least 24 hours apart. Specimens included are nasopharyngeal swab and optional oropharyngeal swab.
- **Pulmonary Clearance**: defined as the time from randomization to the date of pulmonary clearance. This is defined as disappearance of virus from LRT specimen where it has previously been found (induced sputum if available, endotracheal aspirate if available).
- **Duration of Hospitalization**: defined as the date of hospitalization to the date of medical discharge.
- **Ventilatory Support**: For those subjects requiring ventilatory support or supplemental oxygen during the treatment period:
 - Supplemental oxygen-free days
 - The development of respiratory failure requiring invasive or noninvasive mechanical ventilation.
- **SOFA Score**: For those subjects evaluated by Sequential Organ Failure Assessment (SOFA) scores at ICU admission through ICU discharge (for subjects requiring intensive care; mean arterial pressure to be measured with an arterial line). See [Appendix A](#)
 - Organ support, according to the number of days within the 28 days starting Day 1 when subjects do not receive specific forms of support:
 - a. Supplemental oxygen-free days
 - b. Renal replacement therapy-free days
 - c. Vasopressor-free days
 - d. Invasive or non-invasive mechanical ventilation free days
 - e. Organ support-free days (that is, days free of invasive mechanical ventilation, renal replacement therapy and vasopressors)
 - f. Extracorporeal circulation support-free days
- **Mortality**: defined as the death within 28 days and 6 months of any cause.
- **NEWS2 Score**: NEWS2 Score will be calculated based on data collected in the EDC for assessment of clinical symptoms including respiration, oxygen saturation, blood pressure, pulse, consciousness, and temperature ([Royal College of Physicians, 2017, Section 19](#)). See [Appendix C](#).
- **Radiologic Evaluation**: Chest x-ray and/or CT scans will be evaluated at timepoints outlined in the Table of Events [Section 7 Table 3](#). In an effort to apply objective, semi-quantitative methods for radiologic evaluation, the following binary scoring system will be implemented:
 - Score A: Chest x-ray or CT scan: normal (score 0) versus abnormal (score 1)

- Score B: Pleural Effusion: absence (score 0) versus presence (score 1)
- Radiologic Evaluation Score: the sum of Score A and B.

12. ASSESSMENT OF SUBJECTS

12.1. Study Activities and Evaluations

Subject safety will be assessed in all subjects who receive any amount of CYNK-001 and will include AEs, vital signs, body weight measurements, physical examination findings, clinical laboratory test results, infusion site assessments, x-ray or computerized tomography (CT) scan results, electrocardiogram (ECG) interpretations, electroencephalography (EEG) if clinically indicated, pregnancy testing for FCBP, and concomitant medications and procedures will be tabulated and summarized by cohort. Timing of evaluations will be assessed as outlined in the Table of Events, [Section 7 Table 3](#).

All AEs will be reported and recorded in the electronic case report form (eCRF). For serious adverse events (SAEs), an expedited reporting procedure will be used. The rate of AEs, SAEs, abnormal laboratory AEs and vital signs (graded according to the NCI CTCAE Version 5.0) will be measured while the subject is on study.

The ASTCT Consensus Grading for CRS and Neurologic Toxicity Associated with Immune Effector Cells will be used for the purposes of grading of CRS considered associated with CYNK-001 by the Investigator. CRS Grading can be found in [Section 12.6.2](#). Any new CRS event or worsening of a pre-existing CRS event at any grade is an expected event and immediately reportable.

Subjects will be monitored for safety from the time of signing ICF through end of study and will be collected in the eCRF.

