12.3.1.3. Suspected Unexpected Serious Adverse Drug Reaction (SUSAR)

SUSAR is an adverse drug reaction that is both serious and unexpected (per the IB) which, based on the opinion of the investigator and/or sponsor, is felt to have a reasonable suspected causal relationship to an investigational product.

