12.3.1.5. Unexpected Event

An AE or suspected adverse reaction is considered “unexpected” if it is not listed in the investigator brochure or is not listed at the specificity or severity that has been observed. This also means that events listed in the investigator brochure is considered “expected”.

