12.3.1.6. Adverse Event of Special Interest (AESI)

An AE of special interest (AESI) (serious or non-serious) is one of the scientific and medical concern specific to the sponsor’s product or program, for which ongoing monitoring and rapid communication by the investigator to the sponsor could be appropriate. Such an event might require further investigation in order to characterize and understand it. Depending on the nature of the event, rapid communication by the trial sponsor to other parties (e.g., regulators) might also be warranted.

In this study, Immune receptor cell associated Neurotoxicity syndrome (ICANS) and hypersensitivity reactions are the noted AESIs. CRS is listed in the IB as an expected event.

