12.5. Expedited Reporting of Adverse Events

For the purpose of regulatory reporting, Drug Safety will determine the expectedness of events suspected of being related to CYNK-001 based on the IB.

In the United States, all SUSARs will be reported in an expedited manner in accordance with 21 CFR 312.32.

Events of PD for the disease under study (including deaths due to PD for indications that are considered to be fatal) will be assessed as anticipated AEs and will not be reported as expedited safety reports to regulatory authorities.

Celularity or its authorized representative shall notify the Investigator of the following information.

- Any AE suspected of being related to the use of CYNK-001 in this study or in other studies that is both serious and unexpected (i.e., SUSAR);
- Any finding from tests in laboratory animals that suggests a significant risk for human subjects including reports of mutagenicity, teratogenicity, or carcinogenicity.

Where required by local legislation, the Investigator shall notify his/her IRB/EC promptly of these new serious and unexpected AE(s) or significant risks to subjects.

The Investigator must keep copies of all pertinent safety information on file including correspondence with Celularity and the IRB/EC.

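### Protocol 12.1 fixes CRS as expected at every grade, which can conflict with the severity test in 12.3.1.5 and let a severe, related CRS miss expedited reporting

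*Protocol*

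**What the plan says.** Five places in the protocol bear on whether a CRS counts as expected.

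- Section 12.1 settles it for all CRS: "Any new CRS event or worsening of a pre-existing CRS event at any grade is an expected event and immediately reportable".
- Section 12.3.1.5, first sentence, calls an event unexpected "if it is not listed in the investigator brochure or is not listed at the specificity or severity that has been observed".
- Section 12.3.1.5, last sentence, begins "This also means that events listed in the investigator brochure is considered" and ends with the word expected. It does not mention severity.
- Section 12.3.1.6 adds "CRS is listed in the IB as an expected event", with no grade.
- Section 12.5 says that, for regulatory reporting, "Drug Safety will determine the expectedness of events suspected of being related to CYNK-001 based on the IB".

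Section 12.3.1.3 requires a SUSAR to be serious, unexpected by reference to the IB, and reasonably suspected of being caused by the product. Section 12.5 then provides that in the United States "all SUSARs will be reported in an expedited manner in accordance with 21 CFR 312.32". Among adverse events, it lists only those that are serious, unexpected and suspected as related for notification to investigators.

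The SAP (section 14.1) tabulates CRS but sets no rule on expectedness.

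**The concern.** Section 12.1 answers the expectedness question for CRS in advance and without regard to severity. The first sentence of 12.3.1.5 makes the answer depend on severity. Expectedness decides SUSAR status, and SUSAR status decides whether regulators receive an expedited report and whether other investigators are told. A reader who follows 12.1 could therefore close a severe, related CRS as expected without opening the IB.

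The protocol has reason to care about severe CRS. Section 12.6.2 says PNK-007, of which CYNK-001 is a cryopreserved formulation, has been associated with CRS. Section 4.4 describes this as the first study of CYNK-001 in SARS-CoV-2. Section 12.6.2.1 warns that the symptoms overlap with overwhelming infection. Section 6.3 makes CRS of Grade 3 or above a DLT, so the protocol separates severe from mild CRS for DLT purposes but not, in 12.1, for expectedness.

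**Working it through.** The documents state no figure on this point, so the check sets the rules side by side.

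**Step 1: apply each rule to a serious, related CRS.** The IB is not among the documents and the severity at which it lists CRS is not stated. The first column is therefore an assumption, varied over a range.

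| Assumed IB listing of CRS | CRS observed | Under 12.1 | Under 12.3.1.5, first sentence | Same answer? |
|---|---|---|---|---|
| All severities, including fatal | Any | Expected | Expected | Yes |
| Grades 1–2 only | Grade 1–2 | Expected | Expected | Yes |
| Grades 1–2 only | Grade 3–4 | Expected, not a SUSAR | Unexpected, a SUSAR | No |
| Grades 1–2 only | Fatal | Not explicit | Unexpected, a SUSAR | Uncertain |
| Grades 1–3 only | Grade 4 | Expected, not a SUSAR | Unexpected, a SUSAR | No |
| Listed with no severity | Grade 3–4 | Expected | Unclear | Cannot tell |

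The fatal row is marked not explicit because Table 7, the CRS scale adopted in 12.6.2.2, stops at Grade 4. Extending the any-grade wording of 12.1 to a fatal CRS is an inference.

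**Step 2: see whether the other sections settle the conflict.** Section 12.5 points to the IB and to Drug Safety, which favours a check of each event. Section 12.3.1.6 and the last sentence of 12.3.1.5, taken at face value, favour treating a listed term as expected whatever its severity. No section says which statement prevails.

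**Step 3: trace what is lost if 12.1 is followed.** The event fails the unexpected limb of 12.3.1.3. Under 12.5 there is then no expedited report and no notice to investigators.

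**Step 4: list what is not lost.**

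- Any CRS remains immediately reportable (12.1, which names no recipient; the sponsor is the natural reading).
- Every SAE to Study Day 28 goes to Drug Safety within 24 hours regardless of relationship, and the investigator informs the IRB/EC where local law requires (12.4).
- CRS of Grade 3 or above to Study Day 28 is a DLT (6.3), and the DMC Chair is notified of a DLT within 24 hours of the sponsor learning of it (14.11.2).
- Related SAEs go to DMC review in both phases (14.10).

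None of these gives regulators an expedited report or directly alerts investigators at other sites. That is the remaining gap.

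**Step 5: bound the exposure.** Planned CYNK-001 recipients are 14 in Phase I plus 36 in Phase II (6.2): 14 + 36 = 50. SAP section 15 records that 7 were enrolled and dosed before closure. These are subjects at risk, not events affected. The affected set is only CRS that is serious, suspected as related, and more severe than the IB lists. The documents give no rate from which to estimate it.

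**The case against.** A reader might infer from 12.1 that a life-threatening or fatal CRS can never be a SUSAR. The documents do not support that. Section 12.3.1.3 ties unexpectedness to the IB, and 12.5 assigns the regulatory decision to Drug Safety on the same basis. Section 12.1 is a general section on assessments and nothing gives it precedence. Drug Safety could follow 12.3.1.5 and 12.5 and class a CRS more severe than listed as unexpected.

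Three further points can be made for the plan. Section 12.1 may only restate an IB listing that already covers all severities. The last sentence of 12.3.1.5 opens as a consequence of the first, so it can be read as carrying the same severity qualifier. And the protocol's silence on the grades of earlier CRS proves little, because section 4.4 is incomplete in the public copy.

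All of this limits the claim, and the first point defeats the absolute reading. It does not remove the inconsistency. Section 12.1 still states a conclusion that 12.5 reserves for Drug Safety, and it does so for every grade, while the first sentence of 12.3.1.5 requires a severity comparison. A protocol should not depend on its users choosing the right one of two rules.

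**Conclusion.** The concern holds in a conditional form. The expectedness statement in 12.1 is wrong as written, because it fixes for all grades of CRS something that 12.3.1.5 and 12.5 make depend on the IB. This is a wording error in a reporting rule, not a matter of design preference.

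Its size depends on the IB. If the IB lists CRS at all severities, the practical effect is nil. If it lists CRS only at lower severity, a serious, related CRS above that level could be handled as expected and miss expedited reporting and investigator notice. It would be too strong to say that every such event would be misclassified, since that assumes Drug Safety sets aside 12.3.1.5 and 12.5. It would also be too strong to say that severe CRS would go unseen, since the sponsor and DMC routes remain. The point still merits correction because it is safety-relevant and cheap to put right.

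**What to change.** 1. **Section 12.1.** Keep the duty to report every new or worsening CRS immediately, whatever its grade. Replace the expectedness statement with one saying that Drug Safety determines expectedness for each event against the specificity and severity listed in the IB, cross-referring to 12.3.1.5 and 12.5. Simply deleting the phrase about expectedness would not do if it also removed the any-grade scope of the reporting duty.
2. **Section 12.3.1.5, last sentence, and the CRS sentence of 12.3.1.6.** State that a listed event is expected only at the listed specificity and severity.
3. **Check against the IB.** Since the SAP reports closure after 7 subjects were dosed, the sponsor should confirm that any serious, related CRS among them was judged against the severity listed in the IB.

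The cost is three wording edits and a short check, with possibly a few more expedited reports. No dose or clinical management rule changes.

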12.1.1. Study Informed Consent and Eligibility Assessment

Once a subject has been identified due to testing positive for COVID-19, they may be approached for Informed Consent. Once the informed consent has been signed, the subject will be evaluated for eligibility and additional research procedures may be performed as needed.

12.1.2. Demographic/Medical History

Demographics (initials, date of birth, gender, race, and ethnicity – if allowed by local regulations)

Complete medical history (all relevant medical conditions diagnosed/occurring prior to screening should also be included). Baseline signs and symptoms will be recorded as medical history. Where possible, grading of medical history by CTCAE, version 5.0 criteria should be included.

12.1.3. Physical Examination, Performance Status, and Infection Symptoms Assessment

A complete physical examination will be conducted and documented appropriate for the clinical status of the subject's health and infection burden.

It is important that during the course of the physical examination the subject should be assessed for symptoms related to their COVID-19 infection. COVID-19 symptoms include but are not limited to the following: fever, cough, sore throat, nasal congestion, loss of taste or smell, shortness of breath, wheezing, chest pain, ear pain, myalgia, arthralgia, malaise, headache, gastrointestinal symptoms. Given that symptoms associated with infection are critical to study

endpoints, symptoms associated with COVID-19 should be documented at baseline and grade according to CTCAE, version 5.0.

Subject's overall wellbeing and illness related symptoms must be monitored during the study for improvement and/or worsening and should be captured in the EDC. Symptom worsening is to be reported as an AE.

SOFA score must be documented for subjects requiring intensive care (See [Appendix A](#)).

Karnofsky Performance Status (KPS) score will also be collected (See [Appendix B](#)). For subjects receiving CYNK-001, the site of infusion will be assessed as outlined in the Table of Events, [Section 7 Table 3](#).

12.1.4. Vital Signs

Vital signs will be measured, including temperature, systolic and diastolic blood pressure, respiration rate, and pulse and oxygen saturation (SpO₂), per standard institutional practice as outlined in the Table of Events.

Vital signs to be collected from medical record during hospitalization. Once subject is discharged the vital signs should be collected in the outpatient facility where the subject is seen.

Upon discharge, plans should be made for appropriately delegated study staff to have telephone contact with subjects every day between hospital discharge through at least Day 15 visit for safety/AE monitoring. Subjects will be provided with a thermometer, pulse oximeter, and blood pressure monitor for at home collection of temperature, oxygen saturation, and blood pressure with written instructions on their use as well as expectations for self-monitoring. These daily measurements will be reported via telephone to the clinical staff during each daily telehealth visit. During these daily telehealth visits, subjects are to report any new symptoms or worsening of symptoms associated with previously identified adverse events and will also provide the study team with daily vital sign measurements. Any vital signs outside of normal range will be escalated to the clinical site study team and evaluated for appropriate management. The subject will be asked during each call to report any new or worsening symptoms that could be consistent with adverse events since the previous visit or telephone call. The investigator (or appropriately delegated study staff) will determine if medical attention or an unscheduled clinic visit is required. Each telephone call should be carefully documented with date and time of the call in the source documents and reported as appropriate.

On each day of CYNK-001 infusion, vital signs to be collected pre-infusion, approximately 30 minutes after the start of infusion, and approximately 4 hours after the completion of infusion.

On non-infusion days where multiple vital signs are collected throughout the day, vital signs should be captured in the EDC once per day and the worst vitals should be recorded.

Note: Subjects must be monitored for at least 4 hours after completion of each CYNK-001 infusion.

Note: CYNK-001 infusion should be paused or discontinued if there are any signs of an infusion site reaction or signs of an allergic reaction to the study drug. In the case an infusion site reaction or allergic reaction is suspected, the CYNK-001 infusion should be stopped, and vital signs should be taken. Treatment should be provided as clinically indicated and the patient should be monitored for at least 4 hours after the infusion.

12.1.5. Weight

Weight will be measured at baseline and thereafter monitored as outlined in the Table of Events.

12.1.6. Height

Height is requested to be taken at Screening/Baseline as outlined in the Table of Events.

12.1.7. Prior and Concomitant Medications and Procedures

Prior and concomitant medications (including those taken within 28 days of signing ICF, and including contraceptive measures and over-the-counter products), must be recorded along with:

- Reason for use
- Dates of administration including start and end dates
- Dosage information including dose and frequency.

Relevant prior and all concomitant procedures should be recorded. Any intervention associated with SOFA should be carefully documented. Oxygen therapy is permitted and should be carefully documented, including daily level of oxygenation requirements from time of hospital admission to time of hospital discharge.

Note: Consultation with the Medical Monitor is required prior to each CYNK-001 infusion if there is:

- an increase in supplemental oxygen of greater than or equal to 50% from baseline (for first CYNK-001 infusion) or from level at prior CYNK-001 infusion (for second and third CYNK-001 infusion) resulting in oxygen use of greater than 8L. -or-
- a change in the mode of supplemental oxygen delivery with the intention to deliver oxygen more efficiently.

The Medical Monitor will escalate to the Sponsor as appropriate to advise if a subject who is experiencing rapid worsening of disease should proceed to first or subsequent CYNK-001 infusion.

12.1.8. Chest X-Ray

A chest x-ray will be performed at baseline to assess the overall pulmonary health of the subject. Subjects are anticipated to have pulmonary infiltrates associated with their infection. Continued monitoring by chest x-ray is anticipated to occur as outlined in the Table of Events. On days when CYNK-001 treatment is administered, it is preferred that this be performed prior to treatment. Information from these procedures will be collected.

12.1.9. Chest Computed Tomography (CT-Scan)

In some cases, it is anticipated that a chest x-ray will not be sufficient for the clinical diagnosis and monitoring of subjects. A chest CT scan may be performed in lieu or in conjunction with chest x-rays, as deemed appropriate by the treating physician. In the event that a CT scan is performed, it is recommended that this be continued at least weekly if clinically indicated to confirm radiological measurements. Information from these procedures will be collected.

12.1.10. Electrocardiogram (ECG)

12-lead ECG. An ECG will be done as part of the subject's Treatment Eligibility screen and thereafter monitored as outlined in the Table of Events. The ECG will be reviewed by a qualified physician (paper or electronic tracing) and will be available for comparison with subsequent ECGs. The following will be recorded on the eCRF:

- PR interval (msec)
- QRS interval (msec)
- QT interval (msec)
- QTcB (Bazett's formula) and/or QTcF (Fridericia's formula) interval (msec)
- Heart rate (BPM)
- RR interval (msec)
- Overall interpretation of ECG

12.1.11. Electroencephalography (EEG)

In the event that Neurotoxicity is identified, and if indicated, electroencephalography may be performed to clinically assess the nature of the AE. Subjects may have electroencephalography changes, such as generalized or frontal slowing or frontal intermittent rhythmic delta activity, which should not be considered seizures ([Lee, 2019](#)).

